6.1.1. Design Diagram

Figure 1: Design Schematic Studies 747-404/405

6.2. Number of Patients

The Komodo Health database contains administrative claims from >350 US payers, tokenized to allow for patient tracking across payers. Komodo Health claims will be linked through Datavant tokenization to Quest Diagnostics and LabCorp laboratory data, the US National Death Index (NDI), and the Organ Transplant Network (OPTN) transplant registry for additional information and outcome verification. The database contains >100,000 patients with a PBC diagnostic code. The Global PBC registry includes >5,000 patients with PBC recruited from 17 liver centers across 8 countries in Europe and North America. It utilizes the CASTOR trial platform for

electronic case report form (eCRF) collection of medical history, clinical events, and laboratory and treatment data.

Komodo Health: In the current Komodo Health database, there are 395 patients who meet criteria for the OCA treatment group:

- Meet PBC claims diagnostic criteria (1 inpatient or 2 outpatient claims)
- Initiate OCA treatment
- Have evidence of UDCA failure

There are 5916 who meet criteria for the control group (OCA-eligible but not currently OCA-treated)

- Meet PBC claims diagnostic criteria (1 inpatient or 2 outpatient claims)
- Have at least 270 days of UDCA use before elevated ALP and/or TB inclusive of up to 4 instances of elevation (inadequate response) or ≤90 days UDCA use before elevated ALP and/or TB (intolerant)
- Have evidence of ALP >ULN and/or TB >ULN

The Komodo Health data have not yet been linked to LabCorp laboratory data. It is anticipated that these numbers will approximately double with the availability of LabCorp data.

Global PBC Registry: The Global PBC registry data are currently being refreshed. A previous analysis identified that 344 patients who had initiated OCA. Among the >5000 patients not treated with OCA, it is anticipated that >2200 will meet criteria for UDCA failure and for inclusion in the control group (Corpechot 2008, Kumagi 2010).

7. SELECTION OF PATIENTS

7.1. Study Population

All patients who meet diagnostic criteria in each database between 01 Jun 2015 and 31 Dec 2021 and who meet the eligibility criteria will be considered for these studies.

All diagnosis, treatment, laboratory, and procedure codes used to identify patients and define study variables are listed in Appendix A.

The treatment group will be patients with PBC with a history of inadequate response or intolerance to UDCA who initiated OCA in the study window. The control group will be PBC patients with a history of inadequate response or intolerance to UDCA who were eligible but were not treated with OCA (or off-label fibrates) in the study window. The decision to treat a patient with OCA or UDCA is at the discretion of the treating physician and has been made independent from inclusion in each of the databases.

7.1.1. Definition of UDCA Failure

UDCA failure includes both inadequate response to UDCA, and intolerance to UDCA. Inadequate UDCA response is defined as:

- At least 1 measure of ALP and/or TB >ULN; and
- \geq 270 days of UDCA treatment prior to ALP and/or TB elevation

UDCA intolerance is defined as:

• A maximum of 90 days of UDCA use with ALP>ULN and/or TB >ULN.

The first date of prescription of OCA after inadequate UDCA response (ALP>upper limit of normal [ULN] and/or total bilirubin [TB]>ULN after >270 days of treatment) or UDCA intolerance (discontinued UDCA after <90 days despite ALP>ULN and/or TB>ULN) will be defined as the index date for OCA-treated PBC patients. The dates of evidence of inadequate UDCA response or UDCA intolerance during which OCA is not utilized will be used as index dates for the non–OCA-treated comparator group.

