Each time a patient meets the UDCA inadequate response/intolerance definition or the definition of OCA initiation, in addition to all other eligibility criteria, they will contribute an index to the study. Therefore, patients may contribute multiple control indices, and may contribute control indices before OCA initiation, but can contribute only one OCA initiation index. The non–OCA-treated patient indices will be weighted to have the same baseline covariate distribution as the OCA-treated patients at the time of OCA initiation, thus allowing for the estimation of the effect of treatment in the treated patients. The pre-index period is defined as 12 months prior to the index date, and follow-up is until the first occurrence of any component of the composite endpoint. Patients will be censored at dropout/disenrollment from the database, discontinuation of OCA (+90 days), initiation of fenofibrate or bezafibrate, initiation of OCA (for the non–OCA-treated patient -indices), unapproved OCA dose (>10 mg once daily [QD]) for those treated with OCA, or the end of the study period (31 Dec 2021), whichever comes first.

Schematic Diagram Studies 747-404/405:

Number of Patients (planned):

Komodo Health: In the current Komodo Health database, there are 395 patients who meet all of the following criteria for the OCA treatment group:

- Meet PBC claims diagnostic criteria (1 inpatient or 2 outpatient claims)
- Have evidence of UDCA failure
- Have initiated OCA treatment

There are 5916 patients who meet all of the following criteria for the control group (OCA-eligible but not currently OCA-treated)

- Meet PBC claims diagnostic criteria (1 inpatient or 2 outpatient claims)
- Have at least 270 days of UDCA use before elevated ALP and/or TB inclusive of up to 4 instances of elevation (inadequate response) or <90 days UDCA use despite elevated ALP and/or bilirubin (intolerant)
- Have elevated ALP >ULN and/or TB >ULN

The Komodo Health database has not yet been linked to LabCorp laboratory database. It is anticipated that the number of patients in each group will approximately double with the availability of LabCorp data.

Global PBC registry: The Global PBC registry data are currently being refreshed. A previous analysis identified 344 patients who had initiated OCA. Among the >5000 patients not treated with OCA, it is anticipated that >2200 will meet criteria for UDCA failure and for inclusion in the control group (Corpechot 2008, Kumagi 2010).

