7.2. Inclusion Criteria

A patient who meets **all** of the following criteria for a given index date is eligible for inclusion:

- Definite or probable PBC diagnosis
 - Global PBC Registry (consistent with American Association for the Study of Liver Diseases [AASLD] and the European Association for the Study of the Liver [EASL] practice guidelines; Lindor 2009, EASL 2009): presence of ≥2 of the following 3 diagnostic factors:
 - History of elevated ALP levels for at least 6 months
 - Positive antimitochondrial antibody (AMA) titer
 - Liver biopsy finding consistent with PBC
 - Komodo Health claims data: one of the following (Meyers 2010):
 - ≥1 inpatient claim with a PBC admission diagnosis at any position (ie, primary, secondary diagnosis, etc.)
 - ≥ 2 outpatient claims with a PBC diagnosis on separate days
- Inadequate response or intolerance to UDCA (see definitions in Section 7.1)
- Age ≥ 18 years at the index date
- Continuous enrollment and evaluable data for at least 12 months before the index date (inclusive)

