7.4. Group Assignments

Treatment group (OCA-treated): ≥ 1 prescription or medical claim for OCA at or after UDCA failure date. The first date will be the one index date.

Control Group (Non-OCA-treated but eligible for OCA): Each date corresponding to evidence of a patient meeting the definition of UDCA inadequate response or intolerance in which the patient meets the inclusion and exclusion criteria and does not initiate OCA will be an

index date for the non–OCA-treated patient group. Patients may contribute indices to this group before they initiate OCA, but not after OCA index.

A thorough description of methodology underlying group assignment can be found in Section 10.1.1.

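### UDCA intolerance is defined both with and without stopping UDCA, so patients in their first 90 days of ongoing UDCA may or may not count as UDCA failures

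*Combined protocol and SAP*

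**What the plan says.** Section 7.1.1 gives two statements of intolerance. The bullet reads "A maximum of 90 days of UDCA use with ALP>ULN and/or TB >ULN". The paragraph below it, which sets the OCA index date, reads "UDCA intolerance (discontinued UDCA after <90 days despite ALP>ULN and/or TB>ULN". The sentence that follows, on control index dates, mentions intolerance without repeating the discontinuation condition. The synopsis has the same pair: its definitions list matches the bullet, and its methodology text matches the paragraph.

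The criteria given for the 5916 Komodo controls use two further wordings, "≤90 days UDCA use before elevated ALP and/or TB (intolerant" in Section 6.2 and "<90 days UDCA use despite elevated ALP and/or bilirubin (intolerant" in the synopsis. Neither mentions stopping UDCA.

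The inclusion criterion points back to the same place: "Inadequate response or intolerance to UDCA (see definitions in Section 7.1". Section 7.4 makes a control index of "Each date corresponding to evidence of a patient meeting the definition of UDCA inadequate response or intolerance", provided that the patient is otherwise eligible and does not start OCA. An OCA patient needs a prescription on or after the UDCA failure date.

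**The concern.** Under the bullet, a patient who has recently started UDCA, is still taking it and has an ALP or TB that is not yet normal meets the definition of UDCA failure. Under the paragraph, the same patient does not. Such a patient has neither completed the 270 days needed to be judged an inadequate responder nor stopped the drug, and so is not clearly among the OCA-eligible patients whom the control group is meant to represent.

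The bullet reaches both groups, but controls are more exposed. An OCA patient contributes one index, at the OCA prescription, whereas a control contributes one at each qualifying date. The discontinuation wording also appears only in the sentence on the OCA index date. A programmer could therefore apply the stricter rule to OCA patients and the looser one to controls, contrary to Section 4.5.3, which rests the comparison on the same eligibility criteria in both groups. Two teams working on two databases could also choose differently in studies that are called replicates.

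**Working it through.** **1. The statements side by side**

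| Place | Limit on UDCA use | Stop of UDCA required? |
|---|---|---|
| Synopsis, methodology (index dates) | <90 days | Yes |
| Synopsis, Komodo control count | <90 days | Not stated |
| Synopsis, definitions | at most 90 days | Not stated |
| Section 6.2, Komodo control count | ≤90 days before the elevation | Not stated |
| Section 7.1.1, bullet | at most 90 days | Not stated |
| Section 7.1.1, index-date paragraph | <90 days | Yes |

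Two of the six require discontinuation and four do not. Three use a strict limit and three include day 90.

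**2. Does another rule close the gap?** No exclusion in Section 7.3 concerns current UDCA use or time on UDCA. The look-back in Section 7.2 is "Continuous enrollment and evaluable data for at least 12 months before the index date (inclusive", which asks for enrollment and data, not for time on UDCA.

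**3. Consistency with the response rule.** Take a patient on continuous UDCA with a raised ALP throughout, at three illustrative days. On day 60 the bullet makes the patient a failure (60 ≤ 90). On day 120 neither route applies (120 > 90 and 120 < 270). From day 270 the patient is an inadequate responder. Moving in and out of failure without any change in treatment or laboratory status is hard to reconcile with a 270-day response rule. With the discontinuation condition, the day-60 classification does not arise.

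**4. Does weighting deal with it?** The covariates in Section 10.1.1 include time since UDCA failure and liver biochemistry, but neither UDCA duration nor current UDCA use. Appendix B Tables 28 and 30 list UDCA duration in the propensity model and the balance table. The two lists disagree.

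**5. Size and direction of bias.** Let q₁ and q₀ be the shares of ongoing new starters in the OCA group and the weighted control group, and r their event hazard relative to other patients. With constant hazards and the same r and OCA effect throughout, the HR is multiplied approximately by

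[1 − q₁(1 − r)] / [1 − q₀(1 − r)].

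If q₀ > q₁, the HR moves up when r < 1 and down when r > 1; if q₀ = q₁, the factor is 1. The documents give none of these three quantities.

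**6. Cost in power of a stricter definition.** Inputs from Section 10.4: 395 OCA and 5916 controls (Komodo); 344 and 2200 (registry); HR 0.5; alpha 0.05, taken as two-sided; VIF 1.5. With p the OCA share and d = N × event rate / VIF,

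power = Φ(√[d·p(1 − p)] × |ln 0.5| − 1.96).

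The plan calls power adequate for event rates above 6% (Komodo) and 8% (registry). By this formula 80% is reached at 6.6% and 8.2%. At the stated rates:

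- Komodo, 6%: N = 6311, p = 0.0626, d = 252.4; power 76.0%.
- Registry, 8%: N = 2544, p = 0.1352, d = 135.7; power 78.8%.

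Now remove 30% of controls, an assumed upper end of a 0% to 30% range:

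- Komodo: 4141 controls, N = 4536, p = 0.0871, d = 181.4; power 74.9%.
- Registry: 1540 controls, N = 1884, p = 0.1826, d = 100.5; power 76.6%.

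The losses are 1.1 and 2.2 percentage points.

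**The case against.** The strongest reply is that the passages can be read together. The bullet's 90-day maximum may mean total, completed use, with the next paragraph spelling out the same term. That may be the intent, but the text does not say so. The inclusion criterion refers to a section containing both versions, and Section 6.2 counts use before the elevation, which does not imply that use had ended.

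The plan also has safeguards. Tables 1A and 1B count intolerant patients separately. Tables 21 and 22 show UDCA treatment and duration by group before and after weighting. The Clean Room Committee may revise variable definitions before outcomes are opened. These would help to expose the problem, but they do not say which definition applies. Time since UDCA failure, although a covariate, depends on when failure is declared and so on the definition in dispute. Section 10.1.1 describes treatment decision points in terms of inadequate response only, but Sections 6.1, 7.1.1, 7.4 and 7.6 include intolerance.

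Three stronger inferences are not supported:

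- A reader might conclude that the 5916 controls include patients still on UDCA. The count criteria omit discontinuation, but the documents do not show how the count was programmed.
- A reader might conclude that under the discontinuation version the index is back-dated to a laboratory test before the stop was known. Section 7.1.1 indexes on dates of evidence of intolerance, which can equally mean once the stop is evident. The plan leaves this open.
- A reader might conclude that weighting cannot correct the mix. The shells' UDCA duration could help if it is used. The accurate statement is that the weighting as listed in Section 10.1.1 does not reliably address it.

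**Conclusion.** The inconsistency stands and should be resolved before the groups are built. One stated eligibility rule admits patients who have neither failed UDCA over the response period nor stopped it; another excludes them; no other criterion decides between the two. The rule covers both groups, with more weight on controls.

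It is tempting to go further and say that the control group is diluted and the HR biased in a known direction. The documents do not support this: they give neither the number of patients qualifying through intolerance, nor the share still on UDCA, nor their event rate. The finding concerns who is in the comparison. The one quantity that can be bounded is the cost of tightening: about 1 to 2 points of power, given the plan's sample sizes, HR 0.5, VIF 1.5, the stated event rates, one control observation per patient and an assumed loss of up to 30% of controls.

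**What to change.** - Reconcile Sections 6.2 and 7.1.1 and the synopsis (methodology, control count and definitions) to one definition of intolerance, identical for both groups and both databases. Of the two versions already in the plan, the one with the discontinuation condition fits the term intolerance and the 270-day response rule. This is a rule for classifying recorded data, not for treating patients.
- Settle the boundary, <90 or ≤90 days, and likewise >270 or ≥270 days for inadequate response, where the same sections differ.
- State a data rule for when a UDCA stop is established in claims and in the registry. Section 8.3 gives a gap rule for OCA only. Allow an intolerance-based control index only on or after that date, so that no post-index information is used.
- Make the covariate list in Section 10.1.1 agree with Tables 28 and 30 on UDCA duration.
- Recount the control group under the final definition, showing the intolerance route separately.

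The cost is a wording change, one programming rule per database and a recount. Some control indices will drop out, with the small loss of power shown above.

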7.2. Inclusion Criteria

A patient who meets **all** of the following criteria for a given index date is eligible for inclusion:

- Definite or probable PBC diagnosis
 - Global PBC Registry (consistent with American Association for the Study of Liver Diseases [AASLD] and the European Association for the Study of the Liver [EASL] practice guidelines; Lindor 2009, EASL 2009): presence of ≥2 of the following 3 diagnostic factors:
 - History of elevated ALP levels for at least 6 months
 - Positive antimitochondrial antibody (AMA) titer
 - Liver biopsy finding consistent with PBC
 - Komodo Health claims data: one of the following (Meyers 2010):
 - ≥1 inpatient claim with a PBC admission diagnosis at any position (ie, primary, secondary diagnosis, etc.)
 - ≥ 2 outpatient claims with a PBC diagnosis on separate days
- Inadequate response or intolerance to UDCA (see definitions in Section 7.1)
- Age ≥ 18 years at the index date
- Continuous enrollment and evaluable data for at least 12 months before the index date (inclusive)

7.3. Exclusion Criteria

A patient who meets **any** of the following criteria for a given index date is not eligible for inclusion:

- History or presence of other concomitant liver diseases before the index date (inclusive), including:
 - Acute or chronic hepatitis C virus infection
 - Acute or chronic hepatitis B infection

- Primary sclerosing cholangitis
- Active alcoholic liver disease
- Hepatocellular carcinoma
- Hepatorenal syndrome
- Hepatopulmonary syndrome
- Portopulmonary syndrome
- NASH
- History of non-skin malignancy or melanoma before the index date (inclusive)
- History of HIV before the index date (inclusive)
- Medical conditions that may cause non-hepatic increases in ALP:
 - Paget's disease during the 12-month period before the index date (inclusive)
 - Fractures within 3 months before the index date (inclusive)
- Patients with laboratory values indicative of hepatic decompensation or significant hepatobiliary injury before the index date (inclusive):
 - TB >3 mg/dL
 - ALP >10x ULN
 - ALT and/or AST >10x ULN
- History of liver transplant before the index date (inclusive)
- Evidence of OCA, fenofibrate, or bezafibrate use before the index date (inclusive)
- History or presence of any of the following hepatic decompensating events before the index date (inclusive):
 - Variceal bleeding
 - Ascites
 - Hepatic hydrothorax
 - Spontaneous bacterial peritonitis
 - Hepatic encephalopathy

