K70.11	ICD10	Alcoholic hepatitis with ascites
K70.2	ICD10	Alcoholic fibrosis and sclerosis of liver
K70.30	ICD10	Alcoholic cirrhosis of liver without ascites
K70.31	ICD10	Alcoholic cirrhosis of liver with ascites
K70.40	ICD10	Alcoholic hepatic failure without coma
K70.41	ICD10	Alcoholic hepatic failure with coma
K70.9	ICD10	Alcoholic liver disease, unspecified
571.0	ICD9	Alcoholic fatty liver
571.1	ICD9	Acute alcoholic hepatitis
571.2	ICD9	Alcoholic cirrhosis of liver
571.3	ICD9	Alcoholic liver damage, unspecified
C22.0	ICD10	Liver cell carcinoma
C22.8	ICD10	Malignant neoplasm of liver, primary, unspecified as to type
C22.9	ICD10	Malignant neoplasm of liver, not specified as primary or secondary
155.0	ICD9	Malignant neoplasm of liver, primary
155.2	ICD9	Malignant neoplasm of liver, not specified as primary or secondary
K76.7	ICD10	Hepatorenal syndrome
572.4	ICD9	Hepatorenal syndrome
K76.81	ICD10	Hepatopulmonary syndrome
573.5	ICD9	Hepatopulmonary syndrome
I27.21	ICD10	Secondary pulmonary arterial hypertension
K75.81	ICD10	Nonalcoholic steatohepatitis
571.8	ICD9	Other chronic nonalcoholic liver disease
C00	ICD10	Malignant neoplasm of lip
C02	ICD10	Malignant neoplasm of other and unspecified parts of tongue
C03	ICD10	Malignant neoplasm of gum
C04	ICD10	Malignant neoplasm of floor of mouth
C05	ICD10	Malignant neoplasm of palate
C06	ICD10	Malignant neoplasm of other and unspecified parts of mouth
C08	ICD10	Malignant neoplasm of other and unspecified major salivary glands
C09	ICD10	Malignant neoplasm of tonsil
C10	ICD10	Malignant neoplasm of oropharynx
C11	ICD10	Malignant neoplasm of nasopharynx
C13	ICD10	Malignant neoplasm of hypopharynx
C14	ICD10	Malignant neoplasm of other and ill-defined sites in the lip, oral cavity & pharynx
C15	ICD10	Malignant neoplasm of esophagus
C16	ICD10	Malignant neoplasm of stomach
C17	ICD10	Malignant neoplasm of small intestine
C18	ICD10	Malignant neoplasm of colon
C21	ICD10	Malignant neoplasm of anus and anal canal

CODE	ТҮРЕ	DESCRIPTION
C22	ICD10	Malignant neoplasm of liver and intrahepatic bile ducts
C24	ICD10	Malignant neoplasm of other and unspecified parts of biliary tract
C25	ICD10	Malignant neoplasm of pancreas
C26	ICD10	Malignant neoplasm of other and ill-defined digestive organs
C30	ICD10	Malignant neoplasm of nasal cavity and middle ear
C31	ICD10	Malignant neoplasm of accessory sinuses
C32	ICD10	Malignant neoplasm of larynx
C34	ICD10	Malignant neoplasm of bronchus and lung

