C38	ICD10	Malignant neoplasm of heart, mediastinum and pleura
C39	ICD10	Malignant neoplasm of other and ill-defined sites in the respiratory system and intrathoracic organs
C40	ICD10	Malignant neoplasm of bone and articular cartilage of limbs
C41	ICD10	Malignant neoplasm of bone and articular cartilage of other and unspecified sites
C47	ICD10	Malignant neoplasm of peripheral nerves and autonomic nervous system
C48	ICD10	Malignant neoplasm of retroperitoneum and peritoneum
C49	ICD10	Malignant neoplasm of other connective and soft tissue
C50	ICD10	Malignant neoplasm of breast
C51	ICD10	Malignant neoplasm of vulva
C53	ICD10	Malignant neoplasm of cervix uteri
C54	ICD10	Malignant neoplasm of corpus uteri
C56	ICD10	Malignant neoplasm of ovary
C57	ICD10	Malignant neoplasm of other and unspecified female genital organs
C60	ICD10	Malignant neoplasm of penis
C62	ICD10	Malignant neoplasm of testis
C63	ICD10	Malignant neoplasm of other and unspecified male genital organs
C64	ICD10	Malignant neoplasm of kidney, except renal pelvis
C65	ICD10	Malignant neoplasm of renal pelvis
C66	ICD10	Malignant neoplasm of ureter
C67	ICD10	Malignant neoplasm of bladder
C68	ICD10	Malignant neoplasm of other and unspecified urinary organs
C69	ICD10	Malignant neoplasm of eye and adnexa
C70	ICD10	Malignant neoplasm of meninges
C71	ICD10	Malignant neoplasm of brain
C72	ICD10	Malignant neoplasm of spinal cord, cranial nerves and other parts of central nervous system
C74	ICD10	Malignant neoplasm of adrenal gland
C75	ICD10	Malignant neoplasm of other endocrine glands and related structures
C76	ICD10	Malignant neoplasm of other and ill-defined sites
C77	ICD10	Secondary and unspecified malignant neoplasm of lymph nodes
C78	ICD10	Secondary malignant neoplasm of respiratory and digestive organs
C79	ICD10	Secondary malignant neoplasm of other and unspecified sites

CODE	ТҮРЕ	DESCRIPTION
C80	ICD10	Malignant neoplasm without specification of site
140	ICD9	Malignant neoplasm of lip
141	ICD9	Malignant neoplasm of tongue
142	ICD9	Malignant neoplasm of major salivary glands
143	ICD9	Malignant neoplasm of gum
144	ICD9	Malignant neoplasm of floor of mouth
145	ICD9	Malignant neoplasm of other and unspecified parts of mouth
146	ICD9	Malignant neoplasm of oropharynx
147	ICD9	Malignant neoplasm of nasopharynx
148	ICD9	Malignant neoplasm of hypopharynx
149	ICD9	Malignant neoplasm of other and ill-defined sites within the lip, oral cavity, and
177	ЮЛ	pharynx
150	ICD9	Malignant neoplasm of esophagus

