151	ICD9	Malignant neoplasm of stomach
152	ICD9	Malignant neoplasm of small intestine, including duodenum
153	ICD9	Malignant neoplasm of colon
154	ICD9	Malignant neoplasm of rectum, rectosigmoid junction, and anus
155	ICD9	Malignant neoplasm of liver and intrahepatic bile ducts
156	ICD9	Malignant neoplasm of gallbladder and extrahepatic bile ducts
157	ICD9	Malignant neoplasm of pancreas
158	ICD9	Malignant neoplasm of retroperitoneum and peritoneum
159	ICD9	Malignant neoplasm of other and ill-defined sites within the digestive organs and peritoneum
160	ICD9	Malignant neoplasm of nasal cavities, middle ear, and accessory sinuses
161	ICD9	Malignant neoplasm of larynx
162	ICD9	Malignant neoplasm of trachea, bronchus, and lung
163	ICD9	Malignant neoplasm of pleura
164	ICD9	Malignant neoplasm of thymus, heart, and mediastinum
165	ICD9	Malignant neoplasm of other and ill-defined sites within the respiratory system and intrathoracic organs
170	ICD9	Malignant neoplasm of bone and articular cartilage
171	ICD9	Malignant neoplasm of connective and other soft tissue
174	ICD9	Malignant neoplasm of female breast
175	ICD9	Malignant neoplasm of male breast
180	ICD9	Malignant neoplasm of cervix uteri
182	ICD9	Malignant neoplasm of body of uterus
183	ICD9	Malignant neoplasm of ovary and other uterine adnexa
184	ICD9	Malignant neoplasm of other and unspecified female genital organs
186	ICD9	Malignant neoplasm of testis
187	ICD9	Malignant neoplasm of penis and other male genital organs
188	ICD9	Malignant neoplasm of bladder

CODE	ТҮРЕ	DESCRIPTION
189	ICD9	Malignant neoplasm of kidney and other and unspecified urinary organs
190	ICD9	Malignant neoplasm of eye
191	ICD9	Malignant neoplasm of brain
192	ICD9	Malignant neoplasm of other and unspecified parts of nervous system
194	ICD9	Malignant neoplasm of other endocrine glands and related structures
195	ICD9	Malignant neoplasm of other and ill-defined sites
196	ICD9	Secondary and unspecified malignant neoplasm of lymph nodes
197	ICD9	Secondary malignant neoplasm of respiratory and digestive systems
198	ICD9	Secondary malignant neoplasm of other specified sites
199	ICD9	Malignant neoplasm without specification of site
B20	ICD10	Human immunodeficiency virus infection
B21	ICD10	Human immunodeficiency virus [HIV] disease resulting in malignant neoplasms
B22	ICD10	Human immunodeficiency virus [HIV] disease resulting in other specified diseases
042	ICD9	Human immunodeficiency virus [HIV] infection

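### In the Komodo Health study, the Appendix A malignancy codes only partly implement the section 7.3 cancer exclusion, and no malignancy covariate code adjusts for the patients who get through

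*Combined protocol and SAP*

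**What the plan says.** Section 7.3 lists as an exclusion "History of non-skin malignancy or melanoma before the index date (inclusive"). The only malignancy that this leaves eligible is non-melanoma skin cancer.

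Section 7.1 states: "All diagnosis, treatment, laboratory, and procedure codes used to identify patients and define study variables are listed in Appendix A". Section 10.1.1 says the same of the codes for the control variables. For the claims study, Appendix A is therefore the working form of the exclusion and of the covariates.

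The Appendix A exclusion block gives 57 three-character ICD-10 malignancy categories between C00 and C80, and 47 ICD-9 categories between 140 and 199. Both runs end on the same description, "Malignant neoplasm without specification of site".

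All-cause death is a component of the primary composite (section 5.1) and is also analysed on its own (section 10.6).

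**The concern.** The code list should deliver what the criterion says. If it does not, the Komodo cohort will contain patients whom the protocol declares ineligible.

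This matters because of the endpoint. A death from cancer counts as a primary event. Prior or active cancer could also influence whether a new drug is started. A variable that affects both is a confounder, and the plan deals with this one only by exclusion. Where the exclusion leaks, adjustment would have to take over, and Appendix A gives it no malignancy code to work with.

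The planned outputs would not show the leak either. The attrition shell (Appendix B, Table 1A) has no malignancy step, and the balance table (Table 30) has no cancer row.

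**Working it through.** **Step 1: compare the code list with the criterion.** The table shows the rows on either side of each gap in Appendix A.

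| Cancer | ICD-10 rows | ICD-9 rows |
|---|---|---|
| Melanoma (named in 7.3) | C41, then C47 | 171, then 174 |
| Prostate | C60, then C62 | 184, then 186 |
| Thyroid | C72, then C74 | 192, then 194 |
| Lymphoma, leukaemia | ends at C80; next row is ICD-9 140 | ends at 199; next row is B20 (HIV) |
| Rectum, rectosigmoid | C18, then C21 | 154 present |
| Gallbladder | C22, then C24 | 156 present |
| Trachea | C32, then C34 | 162 present |
| Thymus | C34, then C38 | 164 present |

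The ICD-10 list also skips C01, C07, C12, C45–C46, C52, C55 and C58. The gaps lie between consecutive printed rows, so lost text at page breaks does not explain them.

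**Step 2: compare the two code systems.** ICD-9 154 reads "Malignant neoplasm of rectum, rectosigmoid junction, and anus", while the ICD-10 list has only "Malignant neoplasm of anus and anal canal" (C21). ICD-9 156 reads "Malignant neoplasm of gallbladder and extrahepatic bile ducts", while the ICD-10 list has only "Malignant neoplasm of other and unspecified parts of biliary tract" (C24). Trachea and thymus follow the same pattern. The plan treats these sites as grounds for exclusion in one system and drops them in the other, which points to oversight rather than intent.

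**Step 3: look for adjustment.** The covariate that could carry cancer is the Charlson score. Its Appendix A block has no ICD-10 C-category and no ICD-9 code from 140 to 208. One row mentions neoplastic disease (M36.0), but it codes a muscle and skin disorder.

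**Step 4: scale.** The plan states no figure to reproduce here. Section 10.9 gives a bias formula:

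factor on the ratio = (OR × P1 + 1 − P1) / (OR × P0 + 1 − P0)

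Here P1 and P0 are the prevalences of the unmeasured confounder in the OCA and control groups, and OR is its association with the outcome. Section 10.9 takes the hazard ratio as an approximation to the odds ratio. The documents give none of these inputs for cancer, so every value below is an assumption.

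| P1 (OCA) | P0 (control) | OR | Calculation | Factor |
|---|---|---|---|---|
| 3% | 3% | any | equal terms | 1.00 |
| 1% | 2% | 3 | 1.02 / 1.04 | 0.981 |
| 1% | 3% | 3 | 1.02 / 1.06 | 0.962 |
| 1% | 2% | 5 | 1.04 / 1.08 | 0.963 |
| 1% | 3% | 5 | 1.04 / 1.12 | 0.929 |
| 6% | 3% | 2 | 1.06 / 1.03 | 1.029 |
| 6% | 3% | 3 | 1.12 / 1.06 | 1.057 |
| 6% | 3% | 5 | 1.24 / 1.12 | 1.107 |

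**The case against.** The strongest reply is that the practical effect is small, for five reasons.

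- **Most cancers are listed.** Breast, lung, colon, pancreas, liver, ovary, kidney and bladder all have rows. The secondary and unspecified-site rows (C76–C80, 195–199) would also catch some patients whose primary site has no row, such as those with metastases. This stands. A reader might infer that the exclusion is not implemented at all, but the list does not support that; it is incomplete.
- **One study only.** The registry study (747-404) records medical history on an eCRF, and the two studies are analysed separately. This also stands. The gap should not be read as a defect in both.
- **Both groups are treated alike.** The same list applies to OCA and control indices, so the hazard ratio moves only if residual cancer prevalence still differs after weighting. This stands, and it is why the range in the working includes 1.00 and runs both ways.
- **Charlson might carry cancer.** Section 10.1.1 cites a published version of the index, and a score computed from that source might include malignancy. That source is not available here, and the same section says the control-variable codes are those in Appendix A. On the plan's own terms there is no adjustment.
- **Little weight for some sites.** Section 4.1 gives a female-to-male ratio of about 10:1, so prostate cancer adds little. This is fair for prostate, but it does not help with melanoma, blood and lymphatic cancers, thyroid or rectum.

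The Clean Room Committee may revise definitions (section 10.11). Nothing in the current text corrects the list, and no planned table would prompt the committee to look.

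**Conclusion.** The mismatch holds for the Komodo Health study and rests on the text alone. Applied as written, Appendix A would admit some patients whom 7.3 excludes, into an analysis that counts every death and has no malignancy code to adjust for them.

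The effect on the hazard ratio cannot be determined from the documents. Under the assumed inputs the factor runs from 0.93 to 1.11, so a true hazard ratio of 1.00 would appear as anything from 0.93 to 1.11. That is modest beside the hazard ratio of 0.5 on which section 10.4 bases its power statements.

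A reader might infer that the leak favours OCA, because clinicians may be less likely to start it in patients with cancer. The documents give neither cancer prevalence by group nor any evidence on prescribing in such patients. The range 0.93–0.98 is therefore one scenario, no better supported than 1.00 or 1.03–1.11. The point is a code-list error to correct, not a demonstrated bias.

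**What to change.** Complete the Appendix A malignancy list in both ICD-10 and ICD-9 so that it matches 7.3. It should contain all malignant-neoplasm categories, including melanoma and the blood and lymphatic cancers, and omit only non-melanoma skin cancer. Apply the completed list when the Komodo cohort is built.

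Do this before outcomes are unblinded. Section 10.1.2 keeps the event file separate until the groups and weights are final, so the change can be made without knowledge of results. After unblinding, the same correction would be a post hoc change of eligibility.

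The cost is an edit to a table and a few more exclusions. The Komodo planning counts in section 6.2 (395 and 5916) list no malignancy criterion, so they neither show nor rule out that the exclusion had been applied.
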